5.0 Patient Eligibility

Inclusion Criteria:

Patients will be eligible for inclusion in the study if they meet all of the following criteria:

1. Patients must have a diagnosis of high-risk CLL/SLL and be previously treated with up to 3 lines of prior therapy. High-risk CLL and high-risk SLL is defined by the presence of a 17p deletion or 11q deletion or TP53 mutation. Any CLL and SLL patient who has a short remission duration of less than 3 years after prior first-line chemo-immunotherapy, such as the FCR regimen, also fulfills criteria of high-risk CLL/SLL, regardless of the presence or absence of cytogenetic abnormalities.
2. CLL and SLL patients with 17p deletion or TP53 mutation will not be required to have received any prior therapy, given the poor outcome of CLL/SLL patients to standard frontline chemo-immunotherapy, such patients will be eligible if they are untreated or if they have received up to 3 lines of prior therapy.
3. Patients must have an indication for treatment by 2008 IWCLL Criteria

4. Patients age \geq 18 years at the time of signing informed consent. Understand and voluntarily sign an informed consent. Be able to comply with study procedures and follow-up examinations.
5. ECOG/WHO performance status of 0-1.
6. Patients of childbearing potential must be willing to practice highly effective birth control (e.g., condoms, implants, injectables, combined oral contraceptives, intrauterine devices [IUDs], sexual abstinence, or sterilized partner) during the study and for 30 days after the last dose of study drug. Women of childbearing potential include any female who has experienced menarche and who has not undergone successful surgical sterilization (hysterectomy, bilateral tubal ligation, or bilateral oophorectomy) or is not postmenopausal. Post menopause is defined as follows: Amenorrhea \geq 12 consecutive months without another cause and a documented serum follicle stimulating hormone (FSH) level >35 mIU/mL; a male of childbearing potential is any male that has not been surgically sterilized.
7. Adequate renal and hepatic function as indicated by all of the following: Total bilirubin ≤ 1.5 x institutional Upper Limit of Normal (ULN) except for patients with bilirubin elevation due to Gilbert's disease who will be allowed to participate; an ALT ≤ 2.5 x ULN; and an estimated creatinine clearance (CrCl) of > 30 mL/min, as calculated by the Cockcroft- Gault equation unless disease related.
8. Free of prior malignancies for 3 years with exception of currently treated basal cell, squamous cell carcinoma of the skin, or carcinoma "in situ" of the cervix or breast.
9. A Urine Pregnancy Test (within 7 days of Day 1) is required for women with childbearing potential.

Exclusion Criteria:

1. Pregnant or breast-feeding females
2. Treatment including chemotherapy, chemo-immunotherapy, monoclonal antibody therapy, radiotherapy, high-dose corticosteroid therapy (more than 60 mg Prednisone or equivalent daily), or immunotherapy within 21 days prior to enrollment or concurrent with this trial
3. Investigational agent received within 30 days prior to the first dose of study drug or have previously taken PCI-32765. If received any

- investigational agent prior to this time point, drug-related toxicities must have recovered to Grade 1 or less prior to first dose of study drug.
4. Systemic fungal, bacterial, viral, or other infection not controlled (defined as exhibiting ongoing signs/symptoms related to the infection and without improvement, despite appropriate antibiotics or other treatment).
 5. Patients with uncontrolled Autoimmune Hemolytic Anemia (AIHA) or autoimmune thrombocytopenia (ITP)
 6. Patients with severe hematopoietic insufficiency, as defined by an absolute neutrophil count of less than 500/ μ L and/or a platelet count of less than 30,000/ μ L at time of screening for this protocol.
 7. Any other severe concurrent disease, or have a history of serious organ dysfunction or disease involving the heart, kidney, liver or other organ system that may place the patient at undue risk to undergo therapy with PCI-32765 and rituximab.
 8. Significant cardiovascular disease such as uncontrolled or symptomatic arrhythmias, congestive heart failure, or myocardial infarction within 6 months of screening, or any Class 3 or 4 cardiac disease as defined by the New York Heart Association Functional Classification
 9. Significant screening ECG abnormalities including left bundle branch block, 2nd degree AV block type II, 3rd degree block, bradycardia, and QTc > 470 msec
 10. Any serious medical condition, laboratory abnormality, or psychiatric illness that places the subject at unacceptable risk if he/she were to participate in the study.
 11. History of stroke or cerebral hemorrhage within 6 months
 12. Evidence of bleeding diathesis or coagulopathy
 13. Major surgical procedure, open biopsy, or significant traumatic injury within 28 days prior to Day 1, anticipation of need for major surgical procedure during the course of the study.
 14. Minor surgical procedures, fine needle aspirations or core biopsies within 7 days prior to Day 1. Bone marrow aspiration and/or biopsy are allowed.
 15. Serious, non-healing wound, ulcer, or bone fracture.
 16. Treatment with Coumadin. Patients who recently received Coumadin must be off Coumadin for at least 7 days prior to start of the study.
 17. Any chemotherapy (e.g., bendamustine, cyclophosphamide, pentostatin, or fludarabine), immunotherapy (e.g., alemtuzumab, or ofatumumab),

- bone marrow transplant, experimental therapy, or radiotherapy is prohibited during therapy on this study.
18. Use of medications known to prolong QTc interval or that may be associated with Torsades de Pointes (refer to Appendix F) are prohibited within 7 days of starting study drug and during study-drug treatment.
 19. Requires treatment with strong CYP3A4/5 and/or CYP2D6 inhibitors.

6.0 Pretreatment evaluation

Pretreatment evaluation will include a physical examination including vital signs, ECOG/WHO performance status, height and weight and recording of concurrent medications (within 7 days of Day 1).

Clinical laboratory evaluation will include serum chemistry. This will include sodium, potassium, calcium, magnesium, phosphorus, BUN, creatinine, glucose, albumin, total protein, alkaline phosphatase, total bilirubin, ALT, uric acid, and immunoglobulin levels. Beta-2-microglobulin, coagulation studies (Prothrombin Time/PT; Partial Thromboplastin Time/PTT; and International Normalized Ratio/INR) within 7 days of Day 1. Hematology: Complete CBC and differential and peripheral blood lymphocyte subset and immunoglobulin levels (within 7 days of Day 1). Flow cytometry assessment for peripheral CLL cells (CLL panel) and lymphocyte subpopulations (CD3, CD4, CD8, CD19, CD16/56 cells, within 7 days of Day 1).

A Urine Pregnancy Test (within 7 days of Day 1) is required for women with childbearing potential.

Bone marrow aspiration and biopsy within 28 days from Day 1. Bone marrow will be evaluated by flow cytometry for clonality and for IgVH mutation studies (unless known) ZAP-70 expression (unless known), cytogenetic and genomic abnormalities by FISH. Electrocardiogram (within 28 days from Day 1). Patients also will undergo CT scans of the chest, abdomen, and pelvis within 2 months from Day 1. Furthermore, patients will be asked to fill out the European Organisation for Research and Treatment of Cancer Quality of Life Questionnaire C30 (EORTC QLQ-C30) within 7 days of Day 1 (Appendix E).

7.0 Evaluation During Study

- Clinic visits (this will include vital signs and physical exam) at The University of Texas, M.D. Anderson Cancer Center are required weekly (+/- 3 days) during the first 4 weeks. Patients for whom weekly visits at MD

Anderson during the first month of therapy cause a major hardship can have their clinic visits and rituximab infusions on day 8 (+/- 3 days), day 15 (+/- 3 days), and day 22 (+/- 3 days) at their local physician's office. Such exceptions must be approved by the treating physician and the principal investigator. Patients return for follow up and then prior to start of cycles 2, 3, 4, 6, 9 and 12 (+/- 1 month). If patients stay on the study past 12 cycles, they return for clinic visits at The University of Texas, M.D. Anderson Cancer Center for clinical assessment (this will include vital signs and physical exam), and laboratory workup (hematology and clinical chemistry) every 3 months (+/- 1 month) for cycles 13 through 36, and every 6 months (+/- 1 month) thereafter, until disease progression or study discontinuation for other reasons.

- Hematology and serum chemistry: complete blood counts (white blood cell, hemoglobin, platelets and differential) will be monitored once weekly for the first four weeks, and then every four weeks thereafter.
- Serum chemistry: basic metabolic profile (sodium, potassium, chloride, CO₂, BUN, creatinine and glucose) will be monitored once weekly for the first four weeks and then once every four weeks thereafter until the end of cycle 12. If patients stay on the study past 12 cycles, they will have these laboratory tests (hematology and clinical chemistry) done every 3 months (+/- 1 month) for cycles 13 through 36, and every 6 months (+/- 1 month) thereafter during their clinic visit.
- PT, PTT, INR will be monitored after 1, 3, 6, and 12 cycles (+/- 1 month) and if patients stay on the study past 12 cycles, once every 12 cycles (+/- 1 month).
- beta-2-microglobulin, lymphocyte subset, immunoglobulin levels, bone marrow aspiration will be performed and evaluated by flow cytometry after 3, 6 and 12 cycles and if patients stay on the study past 12 cycles, once every 12 cycles (+/- 1 month). If patients' bone marrow tests are consistent with a complete remission, no further bone marrow testing is mandatory, and will be ordered at the treating physicians' discretion.
- CT scans of the chest, abdomen, and pelvis after 3 or 6 cycles, and 12 cycles, and once every 12 cycles thereafter. If patients stay on the study past 24 cycles, once every 12 cycles only inpatients with measurable disease, as determined by the treating physician.

- Optional Quality of Life questionnaires (EORTC QLQ-C30) will be collected after 2 weeks, and after cycles 1, 3, 6, and 12. Please refer to plan for monitoring patients in the study calendar for further details.
- Optional correlative laboratory studies will be done before study entry (within 7 days of Day 1), and after 1 week (+/- 3 days), 2 weeks (+/- 3 days), 4 weeks (+/- 3 days), and after cycles 3, 6, and 12, and in patients who fail to respond to therapy at the time of treatment failure (as determined by the treating physician) or at the time of relapse.
- Post Treatment Evaluations: Follow-up evaluations will occur at 60 days (+/- 14 days) following completion of study drug administration. Patients who achieve complete remissions or partial remissions with stable disease and discontinue therapy will be followed long-term every 120 days (+/- 60 days) for up to 5 years or until disease progression or start of a new treatment. The post treatment laboratory evaluations include hematology and serum chemistry with a complete blood counts (white blood cell, hemoglobin, platelets and differential) and a basic metabolic profile (sodium, potassium, chloride, CO₂, BUN, creatinine and glucose).

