4.0 Treatment Plan

Rituximab (375 mg/m²) will be given intravenously on Day 1, Day 8 (+/- 3 days), Day 15 (+/- 3 days), and Day 22 (+/- 3 days), and then continued once every 4 weeks only on Days 1 (+/- 7 days) during cycles 2 - 6 (+/- 7 days), see Study Calendar, unless patients experience toxicities that warrant early discontinuation

of the rituximab (as determined by the treating physician). There will be no dose modifications of rituximab. PCI-32765 will be started on Day 2 of cycle 1 at a dose of 420 mg (3 x 140-mg capsules) orally once daily with 8 ounces (approximately 240 mL) of water (avoid GRAPEFRUIT JUICE due to CYP450 3A4 inhibition) and will be continued daily. There will be no dose modifications of PCI-32765. The doses and schedule of PCI-32765 is based on prior studies with this drug in patients with CLL and other B cell malignancies. At this dose, the target enzyme, Btk, is fully inhibited. The rituximab doses and schedule are considered standard for treatment of CLL patients. A subject diary will be used to aid with PCI-32765 administration compliance. Treatment duration will be 12 cycles, and it will be possible to continue beyond 12 cycles if there is a significant benefit such as an ongoing PR or CR. Response will be evaluated after three, six and twelve cycles. (Each cycle consists of 28 days, see Study Calendar).

Rituximab should be held for any Grade 4 toxicity or for any rituximab-related, clinically significant, unmanageable Grade 3 adverse events. Rituximab should be held until the adverse event returns to baseline or resolves complete. PCI 32765 should be held for any Grade 3 toxicity. PCI-32765 should be held until the adverse event returns to baseline or resolves complete. After Cycle 1, if PCI-32765 is held for > 28 days, the subject should be discontinued from the study.

Special Handling Instructions

Allopurinol at the dose of 300mg daily will be given during the first one to two weeks of treatment as standard tumor lysis prophylaxis. Unused or expired PCI-32765 will be disposed per institutional policy.

Concomitant Medication: Patients receiving Coumadin are ineligible to participate in this study. Patients who recently received Coumadin must be off this medication for at least 7 days prior to start of the study.

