Table1. Simulation study with maximum 40 patients:

True median PFS	Pr(stop)	Mean number of patients (25%, 75%)
3 months	0.975	23.3 (14, 33)
4 months	0.632	31.8 (24, 40)
5 months	0.240	36.6 (40, 40)
6 months	0.078	38.6 (40, 40)
7 months	0.038	39.1 (40, 40)
8 months	0.018	39.6 (40, 40)

Interim Analysis on Toxicity: The probability of toxicity (grade 3 or 4) will be monitored based on the Bayesian model (beta-binomial) by assuming a priori probability of toxicity following beta(1,1). The trial will be terminated if $\text{Prob}(\text{toxicity} > 0.25 \mid \text{data}) > 0.90$. Following this rule, the trial will be terminated if $(\# \text{ patients with toxicities})/(\# \text{ patients evaluated}) \geq 2/3, 3/6, 4/9, 5/12, 6/15, 7/18, 8/22, 9/25, 10/28, 11/31, 12/35, 13/38, \text{ or } 14/40$. The operating characteristics for toxicity are summarized in Table 2.

Table 2. Operating characteristics based on 10000 simulation study

True Prob(tox)	Pr(stop early)	Median # Pts (25%, 75%)
0.05	<0.01	40 (40, 40)
0.10	0.04	39 (40, 40)
0.15	0.11	36 (40, 40)
0.25	0.41	28 (9, 40)
0.35	0.79	17 (4, 28)
0.45	0.97	9 (3, 10)
0.55	>0.99	6 (3, 7)

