Statistical Analysis: Descriptive statistical analysis will be calculated, including histograms or box-plots, proportions, range, means and standard deviations. A 95% credible interval on response rate will be estimated based on a beta-binomial distribution. Fisher's exact test and Wilcoxon rank test will be used in univariate analyses of categorical (Stage, for example) and continuous variables (Age, for example), respectively. The data analysis will be performed based on the Intent-to-treat. Survival or times to progression functions will be estimated using the Kaplan-Meier method. Toxicity will be reported by type, frequency and severity. Worst toxicity grades per patient will be tabulated for selected adverse events and laboratory measurements. The Department of Biostatistics will provide and maintain a website ("Clinical Trial Conduct") for enrolling patients on this study and evaluating the efficacy monitoring rules described above. The Clinical Trial Conduct website resides on a secure server, and access is gained through usernames and passwords provided to personnel responsible for enrolling patients and updating patient data. The website is accessed through a browser using secure socket layer (SSL) technology. Personnel responsible for enrolling patients on trials will be trained in the use of the trial website, with emphasis on the importance of timely updating of follow-up times and recording of events. The monitoring rules described below will be automatically evaluated each time patient data are updated on the trial website. If the stopping rule is met, the study statistician, research nurse, and principal investigator will each receive an email notification that the stopping boundary has been met.

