- j) Complete blood counts (white blood cell, hemoglobin, platelets and differential) and Serum chemistry: basic metabolic profile (sodium, potassium, chloride, CO2, BUN, creatinine and glucose) will be monitored once weekly for first 4 weeks (+/-3 Days), and then every 4 weeks thereafter. If patients stay on the study past 12 cycles, they will have these laboratory tests (hematology and clinical chemistry) done every 3 months (+/- 1 month) for cycles 13 through 36, and every 6 months (+/- 1 month) thereafter during their clinic visit.
- k) Once every 4 weeks thereafter until the end of cycle 12.
- l) PT, PTT, INR will be monitored after 1,3,6 and 12 cycles (+/- 1 month) and if patients stay on study past 12 cycles, once every 12 cycles (+/- 1 month).
- m) Will be performed and evaluated by flow cytometry after 3, 6 and 12 cycles (+/- 1 month) and if patients stay on study past 12 cycles, once every 12 cycles (+/- 1 month).
- n) If patients' bone marrow tests are consistent with a complete remission, no further bone marrow testing is mandatory, and will be ordered at the treating physicians' direction.
- o) CT scans of chest and abdomen after 3 or 6, and 12 cycles (+/- 1 month), and once every 12 cycles thereafter. If patients stay on the study past 24 cycles, once every 12 cycles only inpatients with measurable disease, as determined by the treating physician.
- p) Questionnaire collected at baseline, after 3, 6, 12 and every 6 cycles.
- q) Optional correlative laboratory studies (blood samples) will be done before study entry, and after weeks 1, 2, 3, 4 (+/- 3 days).
- r) Optional correlative laboratory studies(blood samples) at 12 weeks (cycle 3) (+/- 1 month) only and again in patients who fail to respond to therapy after 6 months or at the time of relapse.

Time and Events Schedule: Screening

Evaluation or Procedure	Screening (60 days)	Screening (30 Days)	Screening (14 Days)	Screening (7 Days)
Clinical Assessments	(Day -60)	(Day -30)	(Day -14)	(Day -7 to -1)
Informed Consent				X
Physical Evaluation ^a				X
ECOG/WHO Eval				X
Height/Weight				X
Concomitant Medications and Treatment				X
Serum Chemistry ^b				X
PT/PTT/INR ^c				X
Hematology ^d				X
CLL Panel ^e				X
Bone Marrow Aspiration and biopsy ^f		X		
Electrocardiogram ^g		X		
CT Scans ^h	X			
Pregnancy Test				X
Optional correlative laboratory studies (blood samples) ^q				X

- a) Includes vital signs (within 7 days of Day 1).

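### ALT, bilirubin, alkaline phosphatase, uric acid, calcium and phosphorus are measured at screening but not scheduled during treatment, so asymptomatic Grade 3-4 changes in them may be missed

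*Combined protocol and SAP*

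**What the plan says.** **Before treatment.** The Section 6.0 chemistry panel is broad. It includes calcium, magnesium and phosphorus as well as "alkaline phosphatase, total bilirubin, ALT, uric acid, and immunoglobulin levels". Entry depends on two of these tests, ALT and total bilirubin (Section 5.0, inclusion criterion 7).

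**During treatment.** Section 7.0 reads "Serum chemistry: basic metabolic profile (sodium, potassium, chloride, CO₂, BUN, creatinine and glucose) will be monitored once weekly" for the first four weeks, then every four weeks to the end of cycle 12, with sparser draws afterwards. Footnote j of the study calendar agrees: "Serum chemistry: basic metabolic profile (sodium, potassium, chloride, CO2, BUN, creatinine and glucose) will be monitored once weekly for first 4 weeks". The post-treatment bullet in Section 7.0 names "a basic metabolic profile (sodium, potassium, chloride, CO₂, BUN, creatinine and glucose" as well.

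**Where toxicity grades are used.** Section 4.0 states "PCI 32765 should be held for any Grade 3 toxicity". The stopping rule in Section 10.0 counts grade 3 or 4 toxicity with no stated limit on type or attribution. The analysis paragraph of Section 10.0 adds "Worst toxicity grades per patient will be tabulated for selected adverse events and laboratory measurements". Section 9.0 sets CTCAE 4.03 as the scale, and Section 1.0 makes tolerability the secondary objective.

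**Tumour lysis.** Section 4.0 provides allopurinol, which "will be given during the first one to two weeks of treatment as standard tumor lysis prophylaxis".

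**The concern.** A safety rule can act only on what is measured. A patient whose ALT rises to Grade 3 without symptoms has a screening value and no scheduled later value. If nobody orders the test for another reason, that patient counts as free of toxicity in the stopping rule and in the tolerability summary. The same applies to uric acid, calcium and phosphorus in the first weeks, when the plan itself gives tumour-lysis prophylaxis.

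The written schedule matters more here because Section 7.0 allows the Day 8, 15 and 22 visits to take place at a local physician's office. There, the protocol's list is likely to decide what is ordered.

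The direction of the error is fixed. Missed events can only lower the observed toxicity rate, which makes the stopping rule less likely to act and tolerability look better than it is.

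**Working it through.** **1. Is the gap real?** The scheduled tests, side by side:

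| Analyte | Screening (6.0) | On treatment (7.0, footnote j) |
|---|---|---|
| Potassium, creatinine | yes | yes, weekly for 4 weeks, then every 4 weeks |
| PT/PTT/INR | yes | yes, after cycles 1, 3, 6 and 12 |
| ALT, total bilirubin, alkaline phosphatase | yes | not scheduled |
| Uric acid, calcium, phosphorus | yes | not scheduled |

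The other scheduled on-treatment blood tests (blood counts, beta-2-microglobulin, lymphocyte subsets, immunoglobulins) do not measure any of the six. The seven-item list appears in the same form in three places, so it is not a stray line.

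**2. How many draws are affected?** Twelve 28-day cycles are 48 weeks. Weeks 1 to 4 give 4 draws. Weeks 8 to 48 at four-week steps give (48 − 8)/4 + 1 = 11. The total is 15 scheduled chemistry draws, none of which includes the six analytes.

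**3. Does the plan's stopping rule reproduce?** With a beta(1,1) prior and r toxic patients among n, the posterior is Beta(1 + r, 1 + n − r). The rule stops when Pr(p > 0.25 | data) > 0.90. Examples: 2/3 gives 0.949, 8/22 gives 0.904 and 14/40 gives 0.933. All 13 printed boundaries pass, and each is the smallest stopping count at its n. An exact binomial recursion, looking after every patient from the third up to 40, compares with Table 2 as follows:

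| True rate | Table 2 Pr(stop) | Recomputed |
|---|---|---|
| 0.15 | 0.11 | 0.106 |
| 0.25 | 0.41 | 0.407 |
| 0.35 | 0.79 | 0.801 |
| 0.45 | 0.97 | 0.975 |

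The rule's arithmetic is sound. The question is only what is fed into it.

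**4. What would under-ascertainment do?** Let p be the true share of patients with grade 3 or 4 toxicity, and m the share whose only such toxicity lies in the unscheduled analytes and goes unseen. The rule then sees q = p − m. The documents give no value for m, so the values below are assumptions.

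| True p | m = 0 | m = 0.02 | m = 0.05 | m = 0.10 |
|---|---|---|---|---|
| 0.25 | 0.407 | 0.328 | 0.226 | 0.106 |
| 0.35 | 0.801 | 0.735 | 0.618 | 0.407 |
| 0.45 | 0.975 | 0.959 | 0.919 | 0.801 |

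At p = 0.35, these losses mean that 0.02/0.35 = 6%, 0.05/0.35 = 14% and 0.10/0.35 = 29% of all toxic patients are recognisable only through the six analytes.

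**The case against.** Several objections have force.

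- **Prior experience.** Section 2.0 reports no significant liver or kidney toxicity with single-agent PCI-32765, and related events of grade 3 or higher in 17% of patients overall. A loss of 10 points from these analytes alone would be hard to square with that. This stands, and it moves the plausible loss towards the low end. It does not close the question: follow-up was short (median 8 months in Phase Ia, under 2 months in Phase Ib), and the combination with rituximab is what this trial is meant to characterise.
- **Partial cover.** Potassium and creatinine are drawn weekly at first, INR is checked after cycles 1, 3, 6 and 12, unscheduled tests are not barred, and reported symptoms must be recorded. A reader might infer that liver or tumour-lysis toxicity cannot be graded at all. The text supports only that some components are unscheduled and may be missed.
- **Which laboratory values count.** Section 9.0 treats an abnormal value as significant only when it needs intervention or treatment, so an asymptomatic Grade 3 value might not be counted even if measured. Section 4.0 also has two hold rules. One covers every Grade 3 toxicity; the other covers listed events, other grade 4 events and grade 3 events that cannot be managed. Both objections stand. They are contradictions to resolve, but a value that is never measured cannot be appraised under any of these rules.
- **Worst-grade table.** It might seem that this table cannot be produced. It covers selected measurements only and names none of the six, so it is not contradicted.
- **Metabolism.** A reader might take clearance by CYP3A4/5 and CYP2D6 as a sign of expected liver toxicity. Section 4.0 uses it only to restrict interacting drugs.

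**Conclusion.** The omission is clear from the text. Six analytes that the plan measures at screening, two of which decide entry, have no scheduled on-treatment measurement, while a drug hold, a trial stopping rule and the secondary objective all depend on toxicity grades. A site that follows the schedule exactly may miss asymptomatic Grade 3-4 liver abnormalities and the uric acid, calcium and phosphorus components of laboratory tumour lysis.

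The size is not known. At a true rate of 0.35, the stopping probability falls from about 0.80 to 0.74, 0.62 or 0.41 for assumed losses of 2, 5 or 10 points, and does not change if nothing is lost. A reader might infer that the rule's chance of stopping is roughly halved. The documents do not support that: it needs the 10-point loss, which is the top of the assumed range.

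The PFS primary endpoint, the stopping boundaries and the sample size are not affected. This should be fixed as a cheap improvement to safety ascertainment.

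**What to change.** In Section 7.0 and calendar footnote j, add ALT, total bilirubin, alkaline phosphatase, uric acid, calcium and phosphorus to the chemistry at the existing on-treatment draws. Immunoglobulins can stay on their own schedule, and the post-treatment panel need not change for this purpose. No new visit and no change to the boundaries or the 40 patients is needed.

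Separately, reconcile the two hold rules in Section 4.0, the sentence on laboratory significance in Section 9.0 and the event definition of the stopping rule in Section 10.0, so that it is clear which laboratory grades count as toxicity for each purpose. That choice belongs to the sponsor and the investigator. It should not be assumed that every laboratory grade enters the stopping rule, because that could redefine its event. By Table 2, moving the counted rate from 0.25 to 0.35 would raise the stopping probability from 0.41 to 0.79.

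The cost is six added analytes on about 15 draws per patient over 12 cycles, which is a small laboratory expense. The reported toxicity rate may be less favourable. Values not measured during treatment cannot be recovered later.

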10.0 Statistical Design

Endpoint and Design: The primary objective of this phase II study is to assess the activity of the combination of the Bruton's tyrosine kinase (Btk) inhibitor PCI-32765 and rituximab in Chronic Lymphocytic Leukemia (CLL) in high-risk CLL patients that have received prior therapy. Untreated CLL patients with high-risk disease based on the presence of a 17p deletion or *TP53* mutation will also be eligible. The primary endpoint is progression-free survival (PFS). Denote the median (T) = m_H , for the historical data (H) and m_E , for the experimental (E) trial, where T is time to progression in month. We assume that, T is distributed exponentially with median m_H , with the historical regimen and median m_E , with the new treatment. Under a Bayesian model, we will further assume that m_H , follows an inverse gamma (IG) prior with parameters (18, 85) reflecting the historical data (i.e., 20 patients with chromosome 17 abnormalities who had a median PFS of 5 months)⁶, and m_E , follows IG(2.25, 6.25) with the same mean as m_H , but with a much larger variance of 100 to reflect much greater uncertainty about PFS. Progression free survival is defined as the time interval from treatment to progressive disease or death, whichever happens earlier. Patients in complete remission (CR), partial remission (PR) or stable disease (SD) are all counted as progression-free. Due to the characteristic activity of PCI-32765, which typically induces a transient lymphocytosis during the first months of therapy⁷, which is not causing any symptoms and which is due to a re-distribution of CLL cells from the tissue compartments (bone marrow, secondary lymphatic tissues) into the peripheral blood, increases in lymphocyte counts can be expected (although in this combination with rituximab are less likely) and will not be considered as a sign of progressive disease.

Interim Analysis on PFS: We will accrue 40 patients and will monitor the PFS continuously, accrual will be terminated early if $\Pr(m_H + 2 \text{ months} < m_E \mid \text{data}) <$

0.01. The design operating characteristics based on 1000 simulations are summarized in Table 1. (Accrual of 40 patients with a rate = 3/month, 6 months additional follow-up). For example, the trial will stop early with 97.5% chance (23.3 patients in average) if the median PFS is 3 months, but stop early with 7.8% chance (38.6 patients in average) if the median PFS is 6 months.

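### Follow-up after stopping drug depends on response, so some patients still at risk for intent-to-treat PFS have no clear follow-up after the 60-day visit

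*Combined protocol and SAP*

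**What the plan says.** **Endpoint (Section 10.0).** "Progression free survival is defined as the time interval from treatment to progressive disease or death, whichever happens earlier". Also: "Patients in complete remission (CR), partial remission (PR) or stable disease (SD) are all counted as progression-free". The analysis is by intent-to-treat, with Kaplan-Meier curves. Stopping drug and starting another treatment are not PFS events.

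**After drug stops (Section 7.0, Post Treatment Evaluations).** For everyone: "Follow-up evaluations will occur at 60 days (+/- 14 days) following completion of study drug administration". Then, for a subset: "Patients who achieve complete remissions or partial remissions with stable disease and discontinue therapy will be followed long-term every 120 days". This longer follow-up runs "for up to 5 years or until disease progression or start of a new treatment".

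**Ways to stop without progression (Section 4.0).** Treatment lasts 12 cycles of 28 days, and "it will be possible to continue beyond 12 cycles if there is a significant benefit such as an ongoing PR or CR". On drug holds: "After Cycle 1, if PCI-32765 is held for > 28 days, the subject should be discontinued from the study".

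**Response timing (Section 8.0).** Response is assessed after 3, 6 and 12 cycles.

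**The concern.** A patient who stops drug without progression is still at risk for the primary endpoint, whatever the best response. Section 7.0 nevertheless makes long-term follow-up depend on response. Patients outside the named categories would be censored at about 60 days after stopping, while responders are followed for up to 5 years.

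If those who stop progress sooner than those who stay on drug, this censoring is informative. The Kaplan-Meier median is then pushed upward against a historical benchmark of 5 months. Progression dates that were never collected are also hard to recover afterwards.

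**Working it through.** No figure in the plan is disputed here. The check sets the sections side by side and then sizes the effect under stated assumptions.

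**1. Who is covered after 60 days?**

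| Patient who stops without progression | Section 7.0 read literally | Read as including SD |
|---|---|---|
| CR or PR | every 120 days | every 120 days |
| SD, no remission | not named | every 120 days |
| Stops before the cycle 3 assessment | not clearly covered | not clearly covered |
| Starts new treatment | follow-up ends | follow-up ends |

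All four rows remain at risk under the Section 10.0 definition. The third row can occur, because the hold rule in Section 4.0 applies from after cycle 1.

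**2. Inputs.** From the documents: 28-day cycles, the 60-day evaluation and 40 patients. Assumed:
- on-drug median M = 5, 7 or 12 months;
- stopping without progression at c = 0.1, 0.5 or 1 times the progression hazard, from day 28;
- a 3-month median from stopping to progression;
- a share f = 0.69 of stoppers followed long-term, the same for all stoppers.

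The value 0.69 equals the 9 responders among 13 patients (1 CR, 8 PR) in the Phase Ia data of Section 2.2. Applying it to stoppers is an assumption.

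**3. Formulas.** λ = ln2/M, γ = cλ, μ = ln2/3 = 0.231 per month, s = 28 days = 0.92 months, w = 60 days = 1.97 months.
- On drug and unprogressed: On(t) = exp(−λt) up to s, then exp(−λt − γ(t − s)).
- Off drug and unprogressed: Off(t) = ∫γ·On(u)·exp(−μ(t − u))du from s to t. Off_w(t) is the same integral over the last w months only.
- True PFS = On + Off.
- The Kaplan-Meier limit has hazard [λ·On + μ·R]/[On + R], with R = f·Off + (1 − f)·Off_w.
- Share lost while unprogressed = exp(−λs) × c/(1 + c) × exp(−μw) × (1 − f).

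**4. Results.** Lost share, lowest case (M = 5, c = 0.1): 0.880 × 0.0909 × 0.634 × 0.31 = 0.016. Highest case (M = 12, c = 1): 0.948 × 0.5 × 0.634 × 0.31 = 0.093. That is about 2 to 9%, or roughly 1 to 4 of 40 patients.

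| On-drug median (months) | Lost, c = 0.1 / 0.5 / 1 | True median, c = 0.1 / 0.5 / 1 | Largest overstatement (months) |
|---|---|---|---|
| 5 | 1.6 / 5.8 / 8.7% | 4.94 / 4.72 / 4.53 | 0.02 |
| 7 | 1.6 / 6.0 / 9.0% | 6.82 / 6.28 / 5.83 | 0.07 |
| 12 | 1.7 / 6.2 / 9.3% | 11.44 / 9.87 / 8.71 | 0.25 |

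**5. Sensitivity.**
- Hazard unchanged after stopping (post-stop median = M): no bias at any M, only lost information.
- Post-stop hazard held at 5/3 = 1.67 times the on-drug hazard: 0.04 to 0.17 months at M = 12.
- Only 38% followed (17 of 45, the pooled response rate in Section 2.2), 3-month post-stop median: about 3 to 19% lost, and at most about 0.04, 0.15 and 0.56 months at M = 5, 7 and 12.
- If stoppers who are not followed progress sooner than those who are, the bias would be larger than shown. The documents have no data on this.

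**6. Stopping at the planned 12 cycles.** Such a patient is seen to (12 × 28 + 60)/30.44 = 13.0 months, so this route cannot bias a median below that.

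**The case against.** - **The plan does follow most patients who matter.** This stands. A reader might infer that everyone is lost at 60 days and arrive at much larger biases. Section 7.0 follows remitters for up to 5 years, so that scenario is not the written plan.
- **The wording is ambiguous, not restrictive.** This stands in part. The phrase on partial remission with stable disease may have been meant to include SD, and the wording on continuing past 12 cycles gives PR and CR only as examples. Patients who stop before the cycle 3 assessment remain unplaced on either reading.
- **Progression is assessed.** A reader might infer from "The post treatment laboratory evaluations include hematology and serum chemistry with a complete blood counts" that follow-up visits consist of blood tests only. That sentence describes laboratory evaluations, and follow-up until progression implies that progression is looked for.
- **The hold rule.** A reader might infer that a long hold ends PFS follow-up. Being discontinued from the study could simply mean coming off drug. This is an ambiguity to reconcile, not a proven conflict.
- **Ending follow-up at new treatment, and the missing censoring rule.** The first is an estimand choice that Section 7.0 states openly. The second, taken alone, is missing detail, and it can be said only of the text available, since the appendices are not included.
- **The futility rule.** A reader might infer that the rule is materially weakened. The documents give no drop-out assumption behind Table 1, and any figure depends on how the looks are modelled, so none is offered here.
- **Dating on drug may matter more.** This stands. If on-drug progression were dated at the planned clinic visits (an assumption), the median would shift by about +2.4, +0.4 and +1.8 months at 5, 7 and 12. That is more than the effect shown here.

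**Conclusion.** The point holds as a minor one. Section 7.0 states a response-dependent rule for long-term follow-up, while Section 10.0 keeps every unprogressed patient at risk for the intent-to-treat primary endpoint. The direction of any bias is upward if stoppers progress sooner than patients who stay on drug. Under the main assumptions the size is negligible near the 5-month benchmark and about a quarter of a month at an on-drug median of 12. It is larger if fewer stoppers are followed and zero if the hazard does not change. The drop-out rate, the post-stop hazard and the share followed are all assumed, so these figures indicate scale and do not predict the result. The documents do not support a claim that the primary result or the futility rule would be seriously distorted. The case for acting is that the gap is cheap to close now and hard to repair later.

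**What to change.** In Section 7.0, extend the existing 120-day follow-up to every patient who stops drug without progression, whatever the best response, including those who stop before the first response assessment. Reconcile Sections 4.0 and 7.0 by stating that stopping drug does not end PFS follow-up. Leave the drug-hold rule and treatment duration unchanged.

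At each contact record progression status, the actual date of progression, the last progression-free date and survival status. If the actual date is unknown, treat the time as interval-censored. Do not use the visit date as the event date: with all stoppers followed every 120 days under the same drop-out assumptions, visit dating would overstate the median by 0.09 to 0.65 months at 5 and 0.17 to 1.10 at 7. That exceeds the bias being removed.

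It is also desirable to collect progression and survival status after new treatment starts, so that PFS can be reported with and without censoring there. The sponsor should state which is primary.

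The cost is a wording change, a few extra contacts and retrieval of outside records for a small number of the 40 patients at one centre.
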